4.2.3. HDRS₁₇ Total Score

Changes in HDRS₁₇ from baseline to Weeks 1, 4, and 8 will be analyzed using the same mixed-effects model with repeated measures (MMRM) as for the primary endpoint in all 3 mITT analysis datasets.

Summary statistics on HDRS₁₇ (changes from baseline) over time by treatment group will be provided for the following subgroups: (1) Screening hsCRP stratification;

(2) TRD status (TRD vs. non-TRD);

Other subgroups such as 5 types of maltreatment (physical abuse, physical neglect, sexual abuse, emotional abuse and emotional neglect) based on CTQ and baseline BMI status (\leq 25 (normal) vs. >25 (abnormal) or \leq 30 (normal) vs. >30 (abnormal)) may also be explored.

In addition, mean time profile plots of $HDRS_{17}$ over time by treatment group will be provided.

4.2.4. Responders and Remitters

Subjects who have HDRS₁₇ score \leq 7are considered as remitters while those who have \geq 50% improvement in HDRS₁₇ total score from baseline at week 12 are considered responders. The response rate or remission rate at Week 12 in sirukumab will be compared with that in placebo using a logistic regression model including baseline HDRS₁₇ score, screening hsCRP stratification, country and treatment.

Response rate or remission rate at Week 12 will be provided by treatment group for the following subgroups:

(1) Screening hsCRP stratification;

(2) TRD status (TRD vs. non-TRD).

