1.4. Sample Size Justification

Approximately 192 subjects will be enrolled in this study, with approximately 96 subjects randomized per treatment group.

The target study population is male and female subjects with MDD who have had a suboptimal response to standard oral antidepressant therapy; have failed no more than 3 antidepressant treatments in the current major depressive episode; approximately 142 subjects with screening hsCRP $\geq 0.300 \text{ mg/dL}$ (SI 3.00 mg/L) and approximately 50 subjects with screening hsCRP<0.300 mg/dL (SI 3.00 mg/L) will be enrolled.

The expected final sample size of 142 for subjects with screening hsCRP ≥ 0.300 mg/dL (SI 3.00 mg/L) was determined based on the assumption of an effect size of at least 0.5 for the HDRS17 (mean change from baseline to week 12 endpoint between the sirukumab and placebo groups of 4 with SD=8). This is considered to be a clinically relevant difference in a population with suboptimal response to standard oral antidepressant therapy. Power is set at 90.0%, with a 1-sided alpha of 0.125 and a 12-week drop-out rate of 25%. It was also assumed that 10% of the randomized subjects would be excluded from the primary efficacy analysis due to having hsCRP ≥ 3.00 mg/L at screening but not at baseline.

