4.1. Analysis Specifications

4.1.1. Level of Significance

Unless otherwise specified, all statistical comparisons will be carried out at a 1-sided significance level of 12.5% and confidence intervals will be presented at 2-sided confidence level of 75% (ie. equivalent to 1-sided confidence level of 87.5%).

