4.1.2. Data Handling Rules

The last observation carried forward (LOCF) method will be applied to the $HDRS_{17}$ total score in the sensitivity analysis.

The LOCF approach will be used for imputing missing visit data in the ITT LOCF sensitivity efficacy analyses. The LOCF calculation will be performed for all scheduled post-baseline time windows in the double-blind phase.

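### Week 12 response and remission are tested by a single-visit logistic regression with no rule for subjects who lack a Week 12 HDRS17 score

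*SAP*

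**What the plan says.** - **Model.** SAP section 4.2.4: "The response rate or remission rate at Week 12 in sirukumab will be compared with that in placebo using a logistic regression model". Its terms are baseline HDRS17, screening hsCRP stratum, country and treatment. Section 4.2.4 and Table 4 place both endpoints at Week 12.
- **Analysis set.** The secondary-endpoint text at the end of section 4.2.2 uses mainly mITT2. Section 2.5.2 admits to mITT2 any randomized, dosed subject with a baseline and at least one double-blind post-baseline HDRS17 total. A Week 12 score is not required.
- **Missing visits.** Section 4.1.2 applies LOCF to the HDRS17 "total score in the sensitivity analysis", and then to an ITT LOCF sensitivity analysis. No ITT set is defined beside mITT1 to mITT3, and the sensitivity analyses in section 4.2.2 do not list LOCF. Sections 4.1.3 and 4.2.1 deal with missing items, not missing visits.
- **Expected dropout.** Section 1.4 plans for "a 12-week drop-out rate of 25"%.
- **Error level.** Section 4.1.1: unless otherwise specified, "all statistical comparisons will be carried out at a 1-sided significance level of 12.5"%.

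**The concern.** A logistic model of one visit uses only records with an outcome at that visit. With no other instruction, a subject who leaves after Week 8 is in mITT2 but not in the fitted model, and the Week 1, 4 and 8 scores are discarded. The primary MMRM keeps that subject and uses those scores. Two analyses of the same scale then rest on different missing-data assumptions, and the plan does not say so.

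If dropout is related to outcome in one arm more than in the other, the completers of the two arms are no longer comparable. The bias can understate or overstate the drug effect. Response and remission support secondary objectives 4, 10 and 11, and at a 1-sided 12.5% level a modest bias can change the conclusion. A silent text also leaves the handling open until after unblinding.

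**Working it through.** **1. Is the 25% a real planning input?** Inputs from section 1.4: "mean change from baseline to week 12 endpoint between the sirukumab and placebo groups of 4 with SD=8"; "Power is set at 90.0%, with a 1-sided alpha of 0.125 and a 12-week drop-out rate of 25"%; and "It was also assumed that 10% of the randomized subjects would be excluded from the primary efficacy analysis".

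- Per arm: n = 2 × [8 × (1.150 + 1.282) / 4]² = 47.3, rounded up to 48, so 96 in total.
- Inflated: 96 / (0.75 × 0.90) = 142.2, which matches the stated 142.
- Check: 142 × 0.90 × 0.75 / 2 = 47.9 per arm, with power 90.3%.

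The 25% is therefore used, but in the calculation for the hsCRP ≥ 3.00 mg/L group.

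**2. How many subjects are affected?** Section 1.4: "Approximately 192 subjects will be enrolled in this study". If the same rate held for all of them, 192 × 0.25 = 48 would have no Week 12 status and 144 (72 per arm) would remain. This is roughly an upper bound. mITT2 already excludes subjects with no post-baseline score. The Week 12 window (section 2.4) runs from Day 71 to the end of the double-blind phase, whose end date can be the early-termination date (section 2.3.1), so late leavers can still have a Week 12 score.

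**3. Does the unstated choice matter?** The SAP gives no response rates, so these are assumed: completers respond at 30% on placebo and 45% on sirukumab.

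| Dropout placebo / sirukumab | Completers only | Missing as non-response |
|---|---|---|
| 25% / 25% | 15.0 points | 0.45 × 0.75 − 0.30 × 0.75 = 11.3 points |
| 20% / 30% | 15.0 points | 0.45 × 0.70 − 0.30 × 0.80 = 7.5 points |
| 30% / 20% | 15.0 points | 0.45 × 0.80 − 0.30 × 0.70 = 15.0 points |

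**4. A bias that can be checked by hand.** This is a deliberate extreme: true response 30% in both arms, every dropout a non-responder, dropout 20% placebo and 30% sirukumab, 96 per arm.

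- Completer rates: 0.30 / 0.80 = 37.5% and 0.30 / 0.70 = 42.9%. Odds ratio: 0.75 / 0.60 = 1.25 instead of 1.00.
- Standard error: √(0.375 × 0.625 / 76.8 + 0.429 × 0.571 / 67.2) = 0.082.
- Rejection probability at 1-sided 12.5%: 1 − Φ(1.150 − 0.054 / 0.082), about 31%. With the dropout rates reversed it is about 3.6%.

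**5. Dropout that follows the Week 8 score.** Large-sample simulation, no treatment effect. Assumptions: placebo response 33%, dropout 25% in each arm, Week 8/Week 12 correlation 0.7, SD of change 8, baseline normal (23, 4) floored at 18, and logistic dropout on the Week 8 score with slopes of about 0.5 to 2 per SD.

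| Outcome-related dropout in | Completers only, odds ratio | Missing as non-response, odds ratio |
|---|---|---|
| Placebo only | 0.73 to 0.88 | 0.76 to 0.90 |
| Sirukumab only, one intermediate slope | 1.25 | 1.21 |
| Both arms, same mechanism | 1.00 | not needed |

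Under no effect, swapping the arms inverts the odds ratio. The sirukumab-only counterpart of the whole first row is therefore 1/0.88 = 1.14 to 1/0.73 = 1.37, and 1.25 lies within it.

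**The case against.** **The plan does not prescribe a completers-only analysis.** This stands. A reader might infer that section 4.2.4 restricts the model to subjects with a Week 12 score, but it does not say so. Responders and remitters are defined by what they achieve, so a subject with no Week 12 score could be read as a non-responder. Secondary objective 4 speaks of a 12-week end point, and section 2.4 lets a visit be reused for the end point, so carry-forward could also be read in. Neither reading is written in section 4.2.4 or Table 4, which say Week 12. Dropping the record is what the software does by default, not a written rule.

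**A quarter of the subjects need not be lost.** This also stands. A reader might take 48 of 192 as the number lost, but it is a planning rate carried over from the hsCRP ≥ 3.00 mg/L group and roughly a ceiling.

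**Bias is not established.** A reader might infer that the comparison is biased, or that it will understate the MMRM result. The SAP gives no dropout reasons by arm, so neither the presence nor the sign of a bias can be read from it. With the same mechanism in both arms there is essentially none.

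**Multiple imputation is not the only defensible rule, and different assumptions for a continuous and a binary endpoint are no error in themselves.** This is fair. That imputation recovers the true odds ratio when dropout depends on Week 8 is also weak evidence, because the imputation model then contains the cause of the dropout. What remains is that non-response is off by nearly as much as completers-only in the same scenarios, and that the earlier scores are already collected.

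**An LOCF version could be derived.** It could, but section 4.1.2 offers LOCF only as a sensitivity analysis.

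**Conclusion.** The gap is real, and the bias is conditional. The SAP sets no handling for a missing Week 12 response or remission status. Its default discards subjects, up to roughly 25% at the planning rate, together with earlier scores that the primary MMRM uses.

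Under the stated assumptions the simulated odds ratio with no effect ran from about 0.73 to 1.25 when outcome-related dropout occurred in one arm only. It was about 1.00 when the mechanism was shared. The 33% response, the 0.7 correlation, the baseline distribution and the dropout slopes are assumptions; only the 25% and the SD of 8 come from the SAP. The figures show what differential dropout could do and do not forecast this trial.

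The primary analysis, its hypothesis and its sample size are unaffected. This is a worthwhile, inexpensive improvement to a secondary analysis.

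**What to change.** In section 4.2.4, before unblinding:

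1. Multiply impute missing Week 12 HDRS17 totals from treatment, country, screening hsCRP stratum, baseline HDRS17 and all post-baseline HDRS17 scores.
2. Derive response and remission in each imputed data set, fit the logistic model already specified, and combine the estimates.
3. Add a sensitivity analysis that counts a missing Week 12 status as non-response and non-remission.

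The cost is a few sentences in the SAP and minor programming, with no new data. The analysis would rely on a missing-at-random assumption, the same as the primary MMRM, so the two results on the scale could be read together.

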The secondary objectives are to include the evaluation of the impact of treatment with adjunctive sirukumab compared to adjunctive placebo, on: (1) overall safety and tolerability (2) anhedonia (as measured by the change in the Snaith Hamilton Pleasure Scale [SHAPS] from baseline to week 12) (3) global severity of symptoms of MDD (as measured by the change in the Clinical Global Impression - Severity [CGI-S] scale from baseline to Week 12) (4) remission (HDRS₁₇ total score \leq 7) and response rates (\geq 50%) improvement in HDRS₁₇ total score from baseline) at 12-week end point (5) subjectreported severity of symptoms of MDD (as measured by the change in the Patient Health Questionnaire [PHQ-9] from baseline to Week 1 and to Week 12) (6) fatigue (as measured by the change in the Functional Assessment of Chronic Illness Therapy-Fatigue [FACIT Fatigue] scale from baseline to Weeks 1, 4, 8 and 12) and (7) to evaluate the efficacy measured by change in the HDRS17 scores following adjunctive sirukumab compared to adjunctive placebo in the Treatment Resistant Depression (TRD) versus non-TRD subjects. (8) Evaluate pharmacokinetics and immunogenicity of sirukumab in subjects with MDD. (9) Evaluate the impact of treatment with adjunctive sirukumab in subjects with screening hsCRP \geq 3.00 mg/L and in those with screening hsCRP<3.00 mg/L based on changes from baseline to Week 12 in HDRS₁₇ total score. (10) Assess the efficacy of sirukumab compared to placebo as adjunctive therapy to an antidepressant in subjects with MDD with screening hsCRP levels <0.300 mg/dL versus those with screening hsCRP levels ≥ 0.300 mg/dL in improving response of depressive symptoms, defined as the proportion of subjects having a \geq 50% improvement in HDRS17 total score from baseline to the end of Week 12. (11) Assess the efficacy of sirukumab compared to placebo as adjunctive therapy to an antidepressant in subjects with MDD with screening hsCRP levels <0.300 mg/dL versus those with screening hsCRP levels $\geq 0.300 \text{ mg/dL}$ in achieving remission of depressive symptoms, defined as the proportion of subjects having a HDRS₁₇ total score ≤ 7 at the end of Week 12. (12) Evaluate whether hsCRP levels correlate with clinical efficacy as measured by the change from baseline to Week 12 in HDRS₁₇ total score.

Exploratory Objectives

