2.6. Definition of Subgroups

Descriptive statistics will be performed for the primary endpoint of HDRS₁₇ change from baseline stratified by the following sub-groups.

- Screening hsCRP stratification (<3.00 mg/L, \geq 3.00 to <5.00 mg/L, \geq 5.00 to <8.00 mg/L and \geq 8.00 mg/L)
- Treatment Resistant Depression (TRD) vs. non-TRD subjects. (TRD is defined as having be treated with ≥ 2 trials of antidepressants of adequate dose and duration during the current episode.)

Other subgroups such as 5 types of maltreatment (physical abuse, physical neglect, sexual abuse, emotional abuse and emotional neglect) based on CTQ and baseline BMI status (\leq 25 (normal) vs. >25 (abnormal) or \leq 30 (normal) vs. >30 (abnormal)) may also be explored.

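### Objectives 7, 10 and 11 compare the sirukumab effect between subgroups, but the SAP plans no estimate or interval for those contrasts, and objective 9 has no modelled effect below 3.00 mg/L.

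*SAP*

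**What the plan says.** **Objectives (section 1.1).** Objective 7 concerns the HDRS17 effect of sirukumab "compared to adjunctive placebo in the Treatment Resistant Depression (TRD) versus non-TRD subjects". Objectives 10 and 11 use the same comparative construction for response and remission, with screening hsCRP below 0.300 mg/dL (3.00 mg/L) set against at or above it. Objective 9 is worded differently: it asks for the HDRS17 effect in each of the two hsCRP groups and does not ask for their difference.

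**Subgroup analyses.** Section 2.6 opens with "Descriptive statistics will be performed for the primary endpoint" and lists TRD status and four screening hsCRP strata. Section 4.2.3 provides summary statistics on HDRS17 change "over time by treatment group will be provided for the following subgroups", namely the hsCRP strata and TRD status. Section 4.2.4 says "Response rate or remission rate at Week 12 will be provided by treatment group for the following subgroups", and lists the same two.

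**Models.** The MMRM in section 4.2.2 has screening hsCRP stratum as a main effect, time-by-treatment as its only interaction, and no TRD term. The logistic model in section 4.2.4 has main effects only and no TRD term.

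**Analysis sets (section 2.5.2).** mITT2 takes all hsCRP levels. mITT3 requires screening hsCRP of at least 3.00 mg/L, and mITT1 requires this at baseline as well. No set isolates the subjects below 3.00 mg/L.

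**The concern.** An objective that sets a treatment effect in one group against the same effect in another is answered by the difference between the two effects, with an interval. Per-arm means or rates by subgroup leave the reader to work out that difference by eye, unadjusted and with no measure of its uncertainty.

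This matters most for hsCRP. The trial plans about 50 subjects below 3.00 mg/L, who do not enter the primary set. For HDRS17, a reader would have an adjusted MMRM effect on one side of the cut and an unadjusted summary on the other. For response and remission, the group at or above 3.00 mg/L is split into three strata, so even the pooled rates that objectives 10 and 11 refer to are not listed as a table.

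The optional subgroup MMRM in section 4.2.2 names childhood maltreatment and BMI. It does not name TRD or hsCRP, the two subgroups that the secondary objectives do name.

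**Working it through.** **1. The plan's own figure.** Inputs from section 1.4: a difference "between the sirukumab and placebo groups of 4 with SD=8"; "Power is set at 90.0" per cent; "with a 1-sided alpha of 0.125 and a 12-week drop-out rate of 25" per cent; and "10% of the randomized subjects would be excluded from the primary efficacy analysis".

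- Per arm: n = 2 × [8 × (1.150 + 1.282) / 4]² = 47.3, rounded up to 48, so 96 evaluable.
- Inflation: 96 / (0.75 × 0.90) = 142.2. The stated 142 is reproduced.

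No stated figure is wrong. The question is which analyses are missing.

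**2. Objective against planned analysis.**

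| Objective | Asks for | Planned |
|---|---|---|
| 7 | HDRS17 effect, TRD versus non-TRD | Per-arm summaries by TRD status |
| 9 | HDRS17 effect in each hsCRP group | At or above 3.00: mITT3 MMRM. Below 3.00: per-arm summary only |
| 10, 11 | Response and remission effect, below versus at or above 3.00 | Per-arm rates in four strata |

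**3. Precision of the hsCRP contrast on HDRS17.** Inputs: about 50 subjects below and 142 at or above 3.00 mg/L (section 1.4). Assumptions: SD 8 in both groups and 1:1 arms within each. The 10% exclusion does not apply here, because mITT2 does not require a baseline hsCRP value.

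SE = 8 × √(2/n_low + 2/n_high), with n per arm; 75% half-width = 1.150 × SE; power for a 4-point difference in effects = Φ(4/SE − 1.150).

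- All evaluable (25 and 71 per arm): SE = 8 × √(0.0800 + 0.0282) = 2.63; half-width 3.0; power 64%.
- 25% dropout (18.75 and 53.25 per arm): SE = 8 × √(0.1067 + 0.0376) = 3.04; half-width 3.5; power 57%.

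**4. The missing half of objective 9.** Below 3.00 mg/L with 25% dropout: SE = 8 × √(2/18.75) = 2.61; 75% half-width = 1.150 × 2.61 = 3.0 points.

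**5. TRD contrast on HDRS17.** The SAP gives no TRD share, so 30% to 50% of 144 completers (192 × 0.75) is assumed.

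- 30%: SE = 16 × √(1/43.2 + 1/100.8) = 2.91.
- 50%: SE = 16 × √(1/72 + 1/72) = 2.67.

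The 75% half-widths are 3.3 and 3.1 points.

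**6. Response and remission.** The SAP gives no rates. For a common rate p, replace the SD with √[p(1 − p)]. For p between 10% and 50%, with dropout between none and 25%, the 75% half-width for the difference in risk differences is about 11 to 22 percentage points.

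**The case against.** **Descriptive reporting may be deliberate.** Sections 2.6, 4.2.3 and 4.2.4 are consistent in choosing it, and with about 19 completers per arm below 3.00 mg/L the contrast is weak: 57% to 64% power for a 4-point difference in effects, even at one-sided 0.125. This stands as a reason not to test formally. It is not a reason to leave out the interval, because the objectives are worded as comparisons and the interval shows how little the data can settle.

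**The plan is not silent on hsCRP.** A reader might infer that hsCRP receives only per-arm summaries. That is wrong at or above 3.00 mg/L, where mITT3 gives a modelled HDRS17 effect at Week 12 (section 4.2.2) and at Weeks 1, 4 and 8 (section 4.2.3). Section 5.2.1 also models Week 12 HDRS17 change, response and remission on screening hsCRP, first in sirukumab subjects and then in placebo subjects, and compares the results. But those models use hsCRP without the two-group split, are fitted separately by arm, and are compared informally with no interaction term. They do not supply the contrasts.

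**Objective 9 is not a between-group question.** It could be read as asking whether the effects differ, but its wording asks for an effect in each group.

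**No discordance rule is planned.** A reader might infer that hsCRP dependence would be declared from significance in one group and not in the other. The SAP plans no test below 3.00 mg/L and has no such rule. A discordance rate would therefore describe a procedure outside the plan, and the precision of the contrast is the relevant size.

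**Conclusion.** The gap is real for three secondary objectives and half of a fourth. For objectives 7, 10 and 11, no estimate or interval of the stated contrast is planned. For objective 9, only the modelled effect below 3.00 mg/L is missing. The documents do not support the wider reading that the SAP ignores dependence on hsCRP, or that it draws conclusions from discordant p-values.

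The size is the precision that would be available and is not planned to be reported: for hsCRP on HDRS17, an SE of about 3.0 and a 75% half-width of about 3.5 points, against an assumed treatment effect of 4. For TRD the SE is about 2.7 to 2.9. These figures rest on SD 8 in every subgroup, 1:1 arms within subgroups, 25% dropout counted as lost information, and an assumed TRD share of 30% to 50%. The primary analysis is not affected. The change should be made, but it does not put the trial's main conclusion at risk.

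**What to change.** - **Section 4.2.3.** In mITT2, fit the MMRM with treatment-by-group and treatment-by-group-by-time terms, plus the lower-order terms these need. Do this once for screening hsCRP below versus at or above 3.00 mg/L and once for TRD versus non-TRD. Report the Week 12 sirukumab-placebo difference in each group and the between-group difference, with 75% CIs. The hsCRP model also supplies the missing half of objective 9.
- **Section 4.2.4.** Add a treatment-by-hsCRP-group term (two levels) to the response and remission logistic models. If cells are too sparse, report the difference in risk differences with a 75% CI instead. Tabulate the pooled rates at or above 3.00 mg/L.
- **Interpretation.** Label these analyses estimation only, and state that effect modification is judged from the between-group contrast. Keep the four-stratum and TRD descriptive tables.

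The cost is SAP wording and four further models (two MMRMs and two logistic models) on data already collected. The downsides are low precision, which must be reported as such, and possible sparse cells for remission in the low-hsCRP group, where the logistic model also adjusts for country and stratum.

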4.2.5. Clinical Global Impression-Severity Scale (CGI-S)

The CGI-S is a clinician -rated scale that assesses the severity of mental illness with scores as follows:

1: normal, not at all ill; 2: borderline mentally ill; 3: mildly ill; 4: moderately ill; 5: markedly ill; 6: severely ill; 7: among the most extremely ill patients.

A higher score implies a more severe condition. Change from baseline in CGI-S score will be calculated.

Descriptive statistics (N, mean, median and range) of the numerical scores and as well changes from baseline will be provided by treatment group.

A frequency distribution of severity scores may be provided by treatment group from Week 1 to Week 12.

In addition, analyses on changes from baseline in CGI-S score may also be conducted using the similar aforementioned MMRM for the primary analyses.

